9.5.2. Sheehan-Suicidality Tracking Scale (S-STs)

The S-STs is a 16-item scale that assesses the seriousness of suicidality phenomena on a Likert-type scale (0-4) ranging from "not at all" (0) to "extremely" (4). It also assesses the frequency of key phenomena and the overall time spent in suicidality. This study is only collecting the total

scale score. S-STS total scores will be summarized descriptively by treatment and visit as both observed values and change from baseline values.

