4.2.2 SECONDARY ENDPOINTS

This study is not powered to detect statistically significant differences in cognitive or motor domains between

the Baseline and End of Study values. Secondary endpoints will be summarized over the study period from Baseline values using descriptive statistics.

Secondary Efficacy Endpoints:

- Change from baseline in the MoCA (Nasreddine 2005)(Appendix 1).
- Change from baseline in Continuity and Power of Attention, Working Memory, and Episodic Memory on the CDR-CCB (Wesnes 1977, Wesnes 2000).
- Change from baseline in D-KEFS Verbal Fluency (Delis 2001, Delis 2004, Emre 2004).
- Change from baseline in the MDS-UPDRS 1, 2, 3, and total score (Fahn 1987, Movement Disorders Task Force 2003)(Appendix 2).
- Change from baseline in the SE-ADL Scale (Schwab 1968)(Appendix 3).
- Change from baseline in the CISI-PD (Martinez-Martin 2006)(Appendix 4).
- Change from baseline in the PDQ-39 (Peto 1998)(Appendix 5).
- Change from baseline in the GDS-15 (Yesavage 1983)(Appendix 6).
- Change from baseline in the dCDT (Müller 2017).

Secondary Safety Endpoints:

- Change from baseline in clinical laboratory parameters.
- Change from baseline in vital sign measurements.
- Change from baseline in body weight.
- Change from baseline in the S-STs (Sheehan 2014)(Appendix 7).

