7.3.1 SCREENING

Visit 1, Screening Visit (Day -35 to -8)

- Informed consent of subject (or the subject's legally authorized representative) as documented by a signed and dated informed consent form must be obtained prior to any study-related assessments.
- Administer the S-STS.
- Administer the MoCA.
- Administer the MHIS.
- Verify diagnosis of PD according to MDS criteria, including Hoehn and Yahr stage.
- Verify diagnosis of PD-MCI or PDD according to the consensus criteria.
- Obtain medical history, including medical records and test results to support PD, PD-MCI, or PDD diagnosis if available.

- Collect demographic information.
- Review subject's current and prior medications.
- Review and provide the subject (and subject's trial partner) with a list of permitted and prohibited medications.
- Collect vital signs (including sitting, supine, and standing BP), height, and weight.
- Perform a complete physical and neurological exam.
- Perform 12-lead ECG.
- Collect blood and urine samples required for the Screening Safety Lab Panel.
- Perform transthoracic echocardiogram.
- Complete screening MRI scan.
- Verify that the subject fulfills all of the inclusion criteria and none of the exclusion criteria.

During the screening period, subjects should complete two training sessions with the CDR-CCB system prior to baseline testing at Visit 2. The two training sessions may be scheduled at any time during the screening window.

Note: The Screening Visit may be split to allow for sufficient time to complete all required procedures. Review AEs and concomitant medications during split visits, as applicable.

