 4. MDS-UPDRS 1/2/3
 5. SE-ADL
 6. CISI-PD
 7. PDQ-39
 8. GDS-15

7.3.4 TREATMENT

There are two treatment periods scheduled during the trial. During each treatment period, subjects will receive a total of 5 infusions of their assigned treatment (i.e., either GRF6021 or placebo). It is anticipated that sites will infuse subjects with 5 doses over 5 consecutive days. A “grace day” is allowed in the event of unanticipated safety or health concerns during each treatment period.

Visits 3-7 (Days 1-5) and 11-15 (Day 85*-89):

*Day 85 has a \pm 7-day window

- Perform the following procedures prior to administering study treatment:
 - Review AEs and concomitant medications.
 - Obtain blood and urine samples for Comprehensive Labs (**Visits 6 and 14 Only**); fasting samples preferred.
 - Obtain samples for proteomics/epigenetics/biobanking; fasting samples preferred (**Visits 3 and 11 Only**).
 - Obtain sample for ApoE testing (**Visit 3 Only**).
 - For WOCBP Only: perform pregnancy testing and review results (**Visits 3 and 11 Only**).
 - Obtain Pre-infusion Safety Lab samples and assess results **prior to the next day’s infusion (Visits 3, 4, 6, 11, 12, and 14 Only)**. When using an i-STAT Handheld Blood Analyzer, the blood sample(s) may be obtained on the same day as the infusion (Visits 4, 5, 7, 12, 13, and 15).
 - Perform targeted physical exam (i.e. auscultation of heart and lungs and assessment of peripheral edema) (**Visits 3, 5, 7, 11, 13, and 15 Only**).
 - Measure body weight in kilograms.
 - Perform 12-lead ECG (**Visit 7, 11, and 15 Only**).
 - Administer the S-STS (**Visit 3 Only**).
 - Collect vital signs (including sitting, supine, and standing BP).
- Administer study treatment and perform safety assessments per the Infusion Administration Manual ([Appendix 11](#)).
- Administer the S-STS after the subject’s final infusion (**Visit 7 Only**).

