2.2.1.2. Secondary Safety Endpoints

The secondary safety endpoints include the following:

- Change from baseline in clinical laboratory parameters.
- Change from baseline in vital sign measurements.
- Change from baseline in body weight.
- Change from baseline in the S-STs.

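### The S-STS secondary safety endpoint rests on a single post-baseline score at about Day 5, so it yields no change score for the second treatment course or the rest of the study

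*SAP*

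**What the plan says.** SAP 2.2.1.2 lists "Change from baseline in the S-STs" as a secondary safety endpoint, and Protocol 4.2.2 does the same. Neither attaches a time limit. SAP 9.5.2 adds that "S-STS total scores will be summarized descriptively by treatment and visit", as observed values and as changes from baseline.

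The timing comes from the visit lists in Protocol 7.3:

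- Section 7.3.1 (screening, Visit 1): "Administer the S-STS".
- Section 7.3.4 gives the scale before infusion at Visit 3 only.
- Section 7.3.4 then says "Administer the S-STS after the subject’s final infusion", marked as applying to Visit 7 only.

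The S-STS does not appear at the second-course visits (11 to 15), at the follow-up visits (8 to 10 and 16 to 18), or at End of Study/Early Termination (Visit 19). The SAP shell for Table 14.3.6.3 agrees: its rows are Visit 1, Visit 3 and Visit 7, with no instruction to continue to later visits.

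Two Protocol statements suggest wider coverage. Section 4.2.2 says that secondary endpoints are summarised across the study period. Section 10.4.4 names the S-STS score among the continuous safety measures to be plotted over time.

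**The concern.** An endpoint written as change from baseline, without a stated horizon, in a 24-week study of two courses will naturally be taken to cover both courses and the follow-up. The schedule gives it one change score, taken on the last day of the first course. Nothing after that can move the endpoint, so an unremarkable result describes the first five days and is silent on repeat exposure.

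The window is also early by the Protocol's own rationale. Section 2.2 describes effects in mice that develop over days to weeks after dosing, with some lasting about three months, and uses this to justify a second course. A Day 5 score comes before most of that period.

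**Working it through.** **Inputs**

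- Visit 3 is Day 1, Visit 7 is Day 5, and the second course runs from Day 85 to Day 89 (Protocol 7.3.4).
- End of Study is Day 168 ± 7, labelled Week 24 (Protocol 7.3.6 and 15.1).
- Planned infusions: 10, in two courses of 5 (Protocol 6.1.8).
- Baseline is the last value before the first dose (SAP 6.1.1). This is the Visit 3 pre-infusion score or, if that is missing, the Visit 1 score.

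**Check of the plan's own figure.** 168 / 7 = 24.0 weeks, which agrees with the Week 24 label.

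**Number of change scores.** Visits 1 and 3 are before the first dose, so Visit 7 is the only post-baseline assessment. Each subject has at most one S-STS change score, about 4 days after baseline.

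**What comes after the last S-STS**

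- Days: 168 − 5 = 163, and 163 / 168 = 97%.
- Weeks: 163 / 7 = 23.3. This divides into 80 days (11.4 weeks) up to Day 85, 4 days from Day 85 to Day 89, and 79 days (11.3 weeks) from Day 89 to Day 168; 80 + 4 + 79 = 163. The 23.3 weeks therefore already contain the second course.
- Infusions: 5 of 10.

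**Sensitivity to the visit windows**

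- Visit 19 at Day 161 or Day 175: (161 − 5) / 7 = 22.3 weeks to (175 − 5) / 7 = 24.3 weeks.
- Adding the ± 7 days at Visit 11, from which later visits are counted: (168 − 14 − 5) / 7 = 21.3 weeks to (168 + 14 − 5) / 7 = 25.3 weeks.
- Grace day, so that the fifth infusion and the S-STS fall on Day 6: (168 − 6) / 7 = 23.1 weeks.
- The schedule table in Protocol 15.1, as extracted from the PDF, puts the post-infusion S-STS mark under Visit 8 (Day 6 + 3). No infusion is given at Visit 8, and both Section 7.3.4 and the SAP shell say Visit 7, so this may be an extraction fault. If Visit 8 were right, the last score would fall on Day 6 to Day 9, leaving (168 − 6) / 7 = 23.1 to (168 − 9) / 7 = 22.7 weeks.

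None of these variants puts a score in or after the second course.

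**Comparison with the other secondary safety endpoints**

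| Endpoint | Last scheduled measurement |
|---|---|
| Clinical laboratory parameters | Visit 19 (exit panel) |
| Vital signs | Visit 19 |
| Body weight | Visit 19 |
| S-STS | Visit 7 |

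The S-STS is the only one of the four that stops after the first course.

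**The case against.** The strongest reply has four parts.

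1. **The limit is already visible.** The Table 14.3.6.3 shell is set out by visit and ends at Week 1 (Visit 7), and it is the only S-STS summary table planned. This stands. It is why a change of wording alone would add little, and why SAP 9.5.2 is not itself in error: the gap lies in the assessment schedule.

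2. **Suicidality is not wholly unobserved.** A reader might infer from the 163 days that nothing relevant is recorded after Day 5. The documents do not support that. Adverse events are reviewed at every visit and TEAEs and SAEs are the primary endpoint, so a recognised event in or after the second course would be reported. The GDS-15 is given at Visits 10 and 18. MDS-UPDRS Part 1, which has a depressed-mood item, is given at Visits 8 to 10 and 16 to 19. These are indirect, however. Adverse-event enquiry uses open questions (Protocol 8.3), none of the 15 GDS items in Appendix 6 asks directly about suicidal thoughts, and none of these sources gives an S-STS change.

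3. **Timing is conventionally left to the schedule.** All the endpoints are worded as change from baseline with no horizon, and the MoCA, for example, ends at Visit 17. The important risks in Protocol 2.3.1 do not include suicidality. This is fair, and it limits the weight of the point. But the MoCA does have a score after the second course, and the S-STS does not.

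4. **An amendment may come late.** The Protocol is version 5.0 of September 2019, and SAP version 4.0 of August 2020 already provides for subjects affected by COVID-19. The documents do not say how many subjects had still to reach Visit 15. This stands as a limit on what the amendment can recover.

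**Conclusion.** The point holds for the S-STS score itself. A named secondary safety endpoint has one post-baseline value, at about Day 5 and after 5 of 10 infusions, with no score in the remaining 163 of 168 days (97%; 23.3 weeks, or 21.3 to 25.3 weeks across the visit windows). That is less than Protocol 4.2.2 and 10.4.4 describe, and less than the other three secondary safety endpoints receive.

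Two stronger readings should be avoided. The second course and the 23 weeks are not separate gaps, because the 23 weeks contain the second course. Nor do the documents plan any claim of reassurance about suicidality for the whole regimen: the S-STS analysis is descriptive and its table shows where the data stop.

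The conclusion assumes that Section 7.3.4 and the SAP shell (Visit 7) are right rather than the extracted schedule table (Visit 8), but it would be nearly the same under Visit 8. The primary endpoint is unaffected. This is an inexpensive improvement to a secondary safety endpoint, not a defect in the main analysis.

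**What to change.** - **Assessment.** Add the S-STS at the existing Visit 15 or 16 and at Visit 19/Early Termination, in Protocol 7.3 and the schedule table, and add those rows to SAP Table 14.3.6.3. The endpoint would then reach the second course and the end of follow-up, and subjects who withdraw early would also have a late score.
- **Wording for subjects already past those visits.** State in SAP 2.2.1.2, SAP 9.5.2 and the report that the endpoint covers baseline to the end of the first course only. If later scores exist for some subjects, show the number contributing at each visit.
- **Reconciliation.** Check the S-STS row of the Protocol 15.1 table against Section 7.3.4, so that both place the post-infusion assessment at the same visit.

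Cost: a few minutes at one or two existing visits for a scale already in use, with no new visits or staff, plus a protocol amendment that helps only subjects who have not yet reached those visits. The wording and the reconciliation are text changes.

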9.6. Concomitant Medication

Prior and concomitant medications, coded using World Health Organization drug dictionary (WHO-DDE) (March 2018), will be summarized descriptively by Anatomical Therapeutic Chemical (ATC) classification Level 4 and PT (i.e., ATC classification Level 5), if applicable, and by treatment group using counts and percentages. Additionally, the number of subjects with prior medications for PD and cognition will be presented by treatment group. Medications for PD will be identified from the indication field on the CRF as well as those in ATC Classes N04, N04A, and N04B. Medications for cognition will be identified by ATC Class N06D and N06DX. A review of prior and concomitant medications along with their indications will be performed prior to database lock.

Prior medications will be presented separately from concomitant medications. The assignment of medications as prior and/or concomitant will be done as follows:

- **Prior medications:** Medications that started before first dose will be considered prior medications whether or not they were stopped before dose.
- **Concomitant medications:** Any medications continuing or starting after the first dose through the end of study will be considered to be concomitant.

If a medication starts prior to the first dose and continues after the first dose it will be considered both prior and concomitant. Prior and concomitant medications will also be listed.

10. Changes from Planned Analysis

The protocol will be amended such that blood pressure values, in conjunction with signs and symptoms of hypo/hypertension, will be at the discretion of the PI as to whether or not they constitute an AESI. As such, ranges for blood pressures of special interest (BPSI) were identified and will be used for consideration in determining whether events are BPSIs going forward. Separate summaries of these measurements will be presented. See Section 9.3.

11. Other Planned Analysis

11.1. Hoehn and Yahr Scale

The Hoehn and Yahr Scale is used to describe the symptom progression of PD. The scale is as follows:

Stage	Description
0	No signs of disease
1.0	Symptoms are very mild; unilateral involvement only
2	Bilateral involvement without impairment of balance

Stage	Description
3	Mild to moderate involvement; some postural instability but physically independent; needs assistance to recover from pull test
4	Severe disability; still able to walk or stand unassisted
5	Wheelchair bound or bedridden unless aided

The Hoehn and Yahr Scale will be assessed at Screening (Visit 1) only and will be listed.

11.2. Modified Hachinski Ischemic Scale (MHIS)

The MHIS is an 8-item scale that examines clinical features that may be consistent with vascular dementia and is commonly used as a screening tool to exclude patients with multi-infarct dementia. Scores for the 8 items are added together for a total score. Subjects who score 5 or greater are more likely to have a dementia of vascular etiology and thus are excluded from participating in this trial.

The MHIS will be assessed at Screening (Visit 1) only and the presence of the clinical features will be listed.

11.3. Echocardiogram

During Screening (Visit 1), an echocardiogram will be performed to evaluate the subject's left ventricular (LV) systolic function to ensure the subject's ejection fraction percentage is $\geq 55\%$. Echocardiogram results will be listed.

12. References

1. US Federal Register. (1998) International Conference on Harmonization; Guidance on Statistical Principles for Clinical Trials. Department of Health and Human Services: Food and Drug Administration [Docket No. 97D-0174]. Federal Register Volume 63, Number 179, pages 49583-49598. September 16, 1998.
2. ASA. (2016) Ethical Guidelines for Statistical Practice. Prepared by the Committee on Professional Ethics, April 2016. <http://www.amstat.org/about/ethicalguidelines.cfm>
3. RSS. (2014) The Royal Statistical Society: Code of Conduct, 2014. <http://www.rss.org.uk/Images/PDF/join-us/RSS-Code-of-Conduct-2014.pdf>.

13. Tables, Listings, and Figures

All listings, tables, and graphs will have a header showing the sponsor company name and protocol and a footer showing the version of SAS, the file name and path, and the source of the data (listing number).

Statistical Analysis Plan,
Sponsor Alkahest, Inc.
Protocol Number ALK6021-201
PCN Number ALKA7951

13.1. Planned Table Descriptions

The following are planned summary tables for protocol number ALK6021-201. The table numbers and page numbers are place holders only and will be determined when the tables are produced.

Table 2: Demographic Data Summary Tables and Figures

Number	Set	Title	Safety IA	Efficacy IA
Table 14.1.1	ITT	Summary of Subject Disposition	X	X
Table 14.1.2.1	ITT	Demographics and Baseline Characteristics	X	X
Table 14.1.3.1	Safety	Summary of Medical History by SOC, PT, and Treatment		
Table 14.1.3.2	Safety	Summary of Parkinson's Disease Medical History by SOC, PT, LLT, and Treatment		
Table 14.1.4	Safety	Summary of Prior Medications by ATC Class Level 4, PT, and Treatment		
Table 14.1.5	Safety	Summary of Exposure by Treatment	X	X

13.2. Efficacy Data Tabulations

Table 3: Efficacy Data

Number	Set	Title	Include in Interim Efficacy Analysis?
Table 14.2.1.1	Evaluable	Summary of Change from Baseline in MoCA Scores by Treatment	X
Table 14.2.1.2	Evaluable	Mean Change from Baseline in MoCA Total Score by Study Visit and Treatment, Tabulation of Fitted Summary Statistics from ANCOVA	
Table 14.2.1.3	Per Protocol	Summary of Change from Baseline in MoCA Scores by Treatment	X
Table 14.2.1.4	Per Protocol	Mean Change from Baseline in MoCA Total Score by Study Visit and Treatment, Tabulation of Fitted Summary Statistics from ANCOVA	
Table 14.2.1.5	Complete	Summary of Change from Baseline in MoCA Scores by Treatment	
Table 14.2.1.6	Complete	Mean Change from Baseline in MoCA Total Score by Study Visit and Treatment, Tabulation of Fitted Summary Statistics from ANCOVA	
Table 14.2.2.1	Evaluable	Summary of Change from Baseline in D-KEFS Total Score by Treatment	
Table 14.2.2.2	Evaluable	Mean Change from Baseline in D-KEFS Total Score by Study Visit and Treatment, Tabulation of Fitted Summary Statistics from ANCOVA	
Table 14.2.2.3	Per Protocol	Summary of Change from Baseline in D-KEFS Total Score by Treatment	

Number	Set	Title	Include in Interim Efficacy Analysis?
Table 14.2.2.4	Per Protocol	Mean Change from Baseline in D-KEFS Total Score by Study Visit and Treatment, Tabulation of Fitted Summary Statistics from ANCOVA	
Table 14.2.2.5	Complete	Summary of Change from Baseline in D-KEFS Total Score by Treatment	
Table 14.2.2.6	Complete	Mean Change from Baseline in D-KEFS Total Score by Study Visit and Treatment, Tabulation of Fitted Summary Statistics from ANCOVA	
Table 14.2.3.1	Evaluable	Summary of Change from Baseline in MDS-UPDRS Parts 1, 2, and 3 and Parts 1-3 Total Scores by Treatment	X
Table 14.2.3.2	Evaluable	Mean Change from Baseline in MDS-UPDRS Parts 1, 2, and 3 and Parts 1-3 Total Score by Study Visit and Treatment, Tabulation of Fitted Summary Statistics from ANCOVA	
Table 14.2.3.3	Per Protocol	Summary of Change from Baseline in MDS-UPDRS Parts 1, 2, and 3 and Parts 1-3 Total Scores by Treatment	X
Table 14.2.3.4	Per Protocol	Mean Change from Baseline in MDS-UPDRS Parts 1, 2, and 3 and Parts 1-3 Total Score by Study Visit and Treatment, Tabulation of Fitted Summary Statistics from ANCOVA	
Table 14.2.3.5	Complete	Summary of Change from Baseline in MDS-UPDRS Parts 1, 2, and 3 and Parts 1-3 Total Scores by Treatment	
Table 14.2.3.6	Complete	Mean Change from Baseline in MDS-UPDRS Parts 1, 2, and 3 and Parts 1-3 Total Score by Study Visit and Treatment, Tabulation of Fitted Summary Statistics from ANCOVA	
Table 14.2.4.1	Evaluable	Summary of SE-ADL by Study Visit and Treatment	
Table 14.2.4.2	Per Protocol	Summary of SE-ADL by Study Visit and Treatment	
Table 14.2.4.3	Complete	Summary of SE-ADL by Study Visit and Treatment	
Table 14.2.5.1	Evaluable	Summary of Change from Baseline in CISI-PD Scores by Treatment	
Table 14.2.5.2	Evaluable	Mean Change from Baseline in CISI-PD Total Score by Study Visit and Treatment, Tabulation of Fitted Summary Statistics from ANCOVA	
Table 14.2.5.3	Per Protocol	Summary of Change from Baseline in CISI-PD Scores by Treatment	
Table 14.2.5.4	Per Protocol	Mean Change from Baseline in CISI-PD Total Score by Study Visit and Treatment, Tabulation of Fitted Summary Statistics from ANCOVA	

Number	Set	Title	Include in Interim Efficacy Analysis?
Table 14.2.5.5	Complete	Summary of Change from Baseline in CISI-PD Scores by Treatment	
Table 14.2.5.6	Complete	Mean Change from Baseline in CISI-PD Total Score by Study Visit and Treatment, Tabulation of Fitted Summary Statistics from ANCOVA	
Table 14.2.6.1	Evaluable	Summary of Change from Baseline in PDQ-39 Scores by Treatment	
Table 14.2.6.2	Evaluable	Mean Change from Baseline in PDQ-39 Total Score by Study Visit and Treatment, Tabulation of Fitted Summary Statistics from ANCOVA	
Table 14.2.6.3	Per Protocol	Summary of Change from Baseline in PDQ-39 Scores by Treatment	
Table 14.2.6.4	Per Protocol	Mean Change from Baseline in PDQ-39 Total Score by Study Visit and Treatment, Tabulation of Fitted Summary Statistics from ANCOVA	
Table 14.2.6.5	Complete	Summary of Change from Baseline in PDQ-39 Scores by Treatment	
Table 14.2.6.6	Complete	Mean Change from Baseline in PDQ-39 Total Score by Study Visit and Treatment, Tabulation of Fitted Summary Statistics from ANCOVA	
Table 14.2.7.1	Evaluable	Summary of GDS-15 Categories by Study Visit and Treatment	
Table 14.2.7.2	Evaluable	Summary of Change from Baseline in GDS-15 Score by Treatment	
Table 14.2.7.3	Evaluable	Mean Change from Baseline in GDS-15 Total Score by Study Visit and Treatment, Tabulation of Fitted Summary Statistics from ANCOVA	
Table 14.2.7.4	Per Protocol	Summary of GDS-15 Categories by Study Visit and Treatment	
Table 14.2.7.5	Per Protocol	Summary of Change from Baseline in GDS-15 Score by Treatment	
Table 14.2.7.6	Per Protocol	Mean Change from Baseline in GDS-15 Total Score by Study Visit and Treatment, Tabulation of Fitted Summary Statistics from ANCOVA	
Table 14.2.7.7	Complete	Summary of GDS-15 Categories by Study Visit and Treatment	
Table 14.2.7.8	Complete	Summary of Change from Baseline in GDS-15 Score by Treatment	

Number	Set	Title	Include in Interim Efficacy Analysis?
Table 14.2.7.9	Complete	Mean Change from Baseline in GDS-15 Total Score by Study Visit and Treatment, Tabulation of Fitted Summary Statistics from ANCOVA	
Table 14.2.8.1	Evaluable	Summary of Change from Baseline in dCDT Score by Treatment	
Table 14.2.8.2	Evaluable	Mean Change from Baseline in dCDT Score by Study Visit and Treatment, Tabulation of Fitted Summary Statistics from ANCOVA	
Table 14.2.8.3	Per Protocol	Summary of Change from Baseline in dCDT Score by Treatment	
Table 14.2.8.4	Per Protocol	Mean Change from Baseline in dCDT Score by Study Visit and Treatment, Tabulation of Fitted Summary Statistics from ANCOVA	
Table 14.2.8.5	Complete	Summary of Change from Baseline in dCDT Score by Treatment	
Table 14.2.8.6	Complete	Mean Change from Baseline in dCDT Score by Study Visit and Treatment, Tabulation of Fitted Summary Statistics from ANCOVA	
Table 14.2.8.7	Evaluable	Summary of dCDT Classification by Study Visit and Treatment	
Table 14.2.8.8	Per Protocol	Summary of dCDT Classification by Study Visit and Treatment	
Table 14.2.8.9	Complete	Summary of dCDT Classification by Study Visit and Treatment	
Table 14.2.9.1	Evaluable	Summary of Screening Safety MRI Results by Treatment	
Table 14.2.9.2	Per Protocol	Summary of Screening Safety MRI Results by Treatment	
Table 14.2.9.3	Evaluable	Summary of Volumetric MRI Results by Treatment	
Table 14.2.9.4	Evaluable	Summary of ASL MRI Results by Treatment	

